## **Introduction**

### **Background and rationale**

Psoriasis is a chronic inflammatory skin disease affecting 2-4% of the adult Western population (1). It is associated with many comorbidities, negatively affects quality of life (2) and is a socio-economic burden for patients and society (3). Topical drugs are the recommended first-line treatment for mild-to-moderate psoriasis, but patient's adherence to treatment is low, which is a barrier to treatment success (4). Poor outcomes result in the need for systemic or biologic treatments that are associated with potential severe adverse events and are often more expensive than topical drugs. Nevertheless, since improved adherence to topical drugs is associated with improved efficacy, there is a need for patient-supporting interventions that improve psoriasis patients' adherence to topical drugs (5, 6).

Patient support by telephone or smartphone applications (apps) may improve adherence to topical treatment, but the effect is small and has only been studied with a short-term follow-up period (7, 8). Furthermore, not all patients have access to a smartphone, and technologies may fail to be sufficiently individualized for all patients' needs.

To improve the effect of topical therapy in psoriasis patients, there is a need for studies on how to optimize the use of available healthcare professionals (9-11). Since dermatologists are a limited resource, the use of dermatology nurses, who are trained to support psoriasis patients in their use of topical drugs, may be a practical solution for improved health outcomes, which can be measured by an objective reduction in the severity of skin disease and may also be reported by patients in patient-reported outcomes (PROs) (in regard to overall health-related quality of life and dermatology-specific quality of life) (12). This is supported by clinical trials and focus group studies suggesting that improved support benefits adherence to topical drugs (13-15). Improved support from dermatology nurses, with specialist training in supporting psoriasis patients may include 1) individualizing treatment plans, 2) providing easy access to dermatology consultation in case of flare-up, and 3) motivating patients to use the medication.

## **Objectives**

The study investigates if the use of topical corticosteroids and/or calcipotriol with a patient-supporting intervention delivered by dermatology nurses supports psoriasis patients' adherence to topical drugs

significantly 1) reduces the severity of psoriasis, 2) improves health-related quality of life, 3) improves long-term adherence to prescribed topical drugs and 4) is cost-effective compared to use of topical corticosteroids and/or calcipotriol with standard patient support.

The null hypothesis is there is no difference in reduction in severity of psoriasis (objectively as measured by the Lattice-System Physician's Global Assessment [LS-PGA]) among psoriasis patients who receive patient-supporting interventions versus those who do not receive the patient-supporting intervention (the non-intervention group). The purpose of the trial is to test the null hypothesis in a superiority setting.

Furthermore (beside the null hypothesis for the primary outcome), the study will also investigate if there is a difference in quality of life (as measured by the PRO Dermatology Life Quality Index [DLQI]), adherence to medication (as measured by filled prescriptions, amount of medication used and reported by patients in a study-specific questionnaire) and health-care costs among those receiving psoriasis patient-supporting interventions versus those who do not receive patient-supporting interventions (the PRO European Quality of life 5 Dimensions [EQ-5D] questionnaire will be obtained in order to answer this research question).

## **Trial design**

The study is a randomized, controlled, investigator-initiated, parallel group with 1:1 allocation ratio, superiority trial (RCT) with an intention to treat (ITT) analysis.

## **Methods: Participants, interventions, and outcomes**

### **Study setting**

The study setting is a single-site study at the outpatient clinic at the Department of Dermatology at Odense University hospital in Denmark. Psoriasis patients who are either already patients at the clinic or newly referred to the clinic will be considered for inclusion.

## **Who will take the informed consent?**

The investigator's first contact with potential participants will take place in an individual face-to-face consultation prior to the baseline visit. Prior to presenting information about the study, the investigator will inform potential participants of their right to make another appointment at which a companion (lay representative) can be present. Potential participants will be provided with oral and written information about the study. The consent will also grant the authorities (the regional Data Protection Agency and the Committee on Health Research Ethics) the right to monitor and check the patients' trial-related data obtained in the electronic research data capture and from the patients' medical chart.

The patient information mentions that the study purpose is to investigate the efficacy of topical drugs, indicates that some participants receive additional nurse-support, stipulates the risks and benefits of the study, potential side-effects, treatment plan, precautions, recording of study relevant data and duty of confidentiality, linkage with register data, audit by authorities (the regional Data Protection Agency and the Committee on Health Research Ethics), access for study personnel (the investigator and study nurses) to enter patients' medical chart and research data tool while the blinded assessor has limited access to the research data tool, compensation and grievance options, finances, voluntary nature of participation, informed consent, and the possibility of withdrawal from the trial. Lastly, the patient will be informed of the availability of treatment if the patient does not wish to participate in the study. Participants shall be made aware of their right to deliberate for 14 days and shall be given the opportunity to have any doubts resolved.

If the patient has decided to participate in the study, the patient in question will date and sign the informed consent and deliver it personally to the investigator. The informed consent is then to be dated and signed by the attesting investigator on the day the patient is informed. The original consent form will be stored in the patient's case report form (CRF).

## **Additional consent provisions for the collection and use of participant data and biological specimens**

The informed consent grants researchers the right to obtain data for research use from the participants medical chart and to link study data to central health registers (for use of medication and other health services) over a two-year period prior to inclusion in the trial and during the trial period.

## **Interventions**

### **Explanation for the choice of comparators**

The non-intervention group receives the standard-of-care treatment for clinical practice at Danish dermatology outpatient clinics. Psoriasis patients are typically seen by a dermatologist at first visit and instructed by a nurse, and every third month thereafter they consult a dermatologist at the outpatient clinic.

### **Intervention description**

#### **Intervention group: Detailed description of the improved patient-support**

The intervention group will include support delivered by three experienced dermatology nurses. Each patient will be supported by the same dermatology nurse throughout the entire study period. The intervention is expected to encourage psoriasis patients to apply the topical drugs on a regular basis by 1) ensuring that patients have a reminder system (16, 17), 2) making patients accountable (18-20), 3) providing support (21), 4) building trust in the treatment and healthcare-provider (10, 13, 22, 23), and 5) by increasing perceived ease of use via favourable comparisons to other treatment options (18, 24). Participants in the intervention group will be seen by a nurse in the dermatology clinic at baseline and weeks 12, 24, 36 and 48. Furthermore, the participants will either be seen in the dermatology clinic or receive follow-up from the nurse by telephone at weeks 1, 4, 8, 16, 20, 28, 32, 40 and 44.

#### **Intervention group: description of study visits**

**Baseline visit** (expected duration: 60 min.) (physician 20 min. and nurse 40 min.): participants are first met by a physician in the dermatology clinic. After obtaining informed consent, patient history and making an objective assessment of the skin, the physician will instruct the patient about topical treatment options and prescribe a

topical treatment after shared decision-making (25). Then, a nurse will instruct the patient on how to use the prescribed topical drugs.

**Consultation by nurse in the clinic or digital follow-ups at weeks 1, 4, 8, 16, 20, 28, 32, 40 and 44**  
(expected duration: 20 min.) (nurse): Participants choose whether they wish to meet the nurse in the clinic or be contacted via telephone, where they may ask questions regarding their treatment and receive further instructions.

**Visits at weeks 12, 24, 36 and 48** (expected duration: 30 min.). Participants are seen by the dermatologist and a nurse in the clinic, questions are answered, and adjustment of topical treatment is introduced as needed.

#### **Non-intervention group: standard-of-care patient support**

The non-intervention group gets the standard-of-care treatment for clinical practice at Danish dermatology outpatient clinics. Psoriasis patients are typically seen by a dermatologist at first visit and instructed by a nurse, and thereafter every third month they consult a dermatologist at the outpatient clinic.

**Visit at baseline and weeks 12, 24, 36 and 48:** At baseline, the participant receives 20 min. instruction from the dermatologist and a possible 15 min instruction from the nurse. Subsequent visits consist of a 15 min dermatologist consultation.

#### **Study drugs**

In both groups, the participants will be prescribed topical drugs based on a shared decision between the prescriber and patient, since preferences for topical drugs differ between patients and there is no single topical drug that is suitable for all psoriasis patients (26). For both groups, one of the topical drugs containing corticosteroids or calcipotriol registered in Denmark for psoriasis patients will be prescribed, since these drugs are the most frequently prescribed topical drugs in Denmark (27) and have a clear dose recommendation (28). All participants will be instructed how to use the medication according to “the fingertip unit for topical steroids”, i.e., 0.5 gram per day per BSA, for as long as a rash is present (28). No placebo or reference compounds will be used in the trial.

The treatment is not prescribed in accordance with a study protocol, but in accordance with common practice. No extra diagnostic or safety measures will be conducted other than standard care, where the

physician informs the patient about common, non-serious as well as rare, serious adverse events and about how to act if these are found.

#### **Description and justification of dose level, dose regimen and frequency plus treatment period**

Patients will be treated once daily as long as a flare is present. When calcipotriol-containing topical drugs are prescribed, maximum consumption will be 15 g/day. Since all patients will be prescribed the same group of recommended standard drugs, it is estimated that there are no increased risks connected with participating in the trial.

#### **Criteria for discontinuing or modifying allocated interventions**

Modifications to allocated interventions will not be permitted.

#### **Strategies to improve adherence to interventions**

On a weekly basis, the investigator will check if the nurses are providing the planned patient-support and are adhering to the protocol. If the nurses do not adhere to the study protocol, the investigator will immediately contact the study nurse and arrange a meeting, where the study nurse will be instructed about the study intervention guide and asked the reason for non- adherence to the study protocol. Furthermore, participants' adherence to prescribed medication will be monitored at visit week 48. Visit adherence may be improved by sending SMS reminders to all study participants a few days before each visit. Adherence to treatment is not improved besides the study intervention allocated to the intervention group.

#### **Relevant concomitant care permitted or prohibited during the trial**

Participants are not allowed to start systemic antipsoriatic drugs prescribed on dermatological indication during the intervention period, since systemic drugs will influence the primary outcome (change in LS-PGA). However, participants who are in a stable phase of prescribed systemic drugs prescribed on dermatological indication at baseline are allowed to be included and kept on the systemic drugs.

## **Provisions for post-trial care**

Participants discontinued from the study due to the occurrence of an SAE will be followed in the relevant medical department. Participants who participate in the study are covered by the Danish Health Authorities via the Danish Act on the right to Complain and Receive Compensation.

## **Outcomes**

Outcome measures will be either assessor-blinded LS-PGA and secondary adherence measures of weight of topical drugs used or patient-reported (for patient-reported adherence, DLQ, and EQ-5D). Below, five elements are specified in full for each outcome: i) domain, ii) specific measure, iii) specific metric, iv) method of aggregation, and v) time-points) (29, 30).

### **Adherence measures**

#### **Primary adherence**

*Specific measure:*

Primary adherence will be measured by the proportion of patients who collect their prescribed topical drug (containing corticosteroid or calcipotriol in the trial period within a certain Anatomical Therapeutic Chemical [ATC] class) from a pharmacy during the study period.

*Specific metric:*

Value at last patient visit.

*Method of aggregation:*

Mean.

*Time point:*

Investigated at visit in week 48.

#### **Secondary adherence**

*Specific measure:*

Secondary adherence will be calculated by combining measured amount of medication used (determined by the weight of the remains in the used medication packages) per body surface area unit affected.

Estimated recommended consumption of medication will be 0.5 gram per day multiplied by the estimated mean BSA during the whole study period, calculated from BSA measures at baseline and at weeks 12, 24, 36 and 48.

$$\text{Rate of secondary adherence} = \frac{\text{Consumed amount of topical drugs}}{\text{Expected amount used}}$$

Consumed amount of topical drugs = Sum of weight of prescribed topical drugsa – sum of weight of all prescribed medication packages returned at visit week 48b.

a: As weighed from representative full medication packages of the prescribed topical drugs.

b: By weight of medication packages returned by blinded assessor when weighed in the outpatient clinic.

Topical drugs (expected amount used) =

$$0.5 \text{ g/day} * 48 \text{ weeks} * 7 \text{ days/week} * \left( \frac{\text{BSA}(\text{baseline}) + 2(\text{BSA}(\text{W12}) + \text{BSA}(\text{W24}) + \text{BSA}(\text{W36})) + \text{BSA}(\text{W48})}{8} \right)$$

*Specific metric:*

Value at last patient visit.

*Method of aggregation:*

Mean.

*Time point:*

The rate of secondary adherence will be assessed at week 48. The measures used to calculate secondary adherence will be obtained as follows: the BSA (1 BSA equals 1% of a person's total body surface area) will be assessed at each visit (baseline, week 12, 24, 36 and 48) while weight of consumed drugs will be obtained at the last visit in week 48.

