### **Plans to promote participant retention and complete follow-up**

All participants receive an automatically generated notification a week prior to attending in the outpatient clinic. In case of non-attendance, the investigator will contact the participant by telephone and suggest a new consultation.

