#### Analysis of secondary outcomes: changes in DLQI value and adherence

Changes in DLQI measures from baseline to weeks 12, 24, 36 and 48 will be compared between the two groups by linear mixed model for longitudinal data. DLQI will be presented in box plots and bar charts.

For separate analyses of the three adherence measures (by filled prescriptions, weight of medication and patient reported adherence, respectively), the adherence rate is dichotomized with a selected cut-off of 80%, with adherence rates above 80% considered adherent (a cut-off typically used when studying adherence in chronic diseases) (8, 42). Dichotomized adherences are compared by using logistic regression.

Statistical analysis will be conducted by an experienced statistician. The statistician will not be blinded to the intervention, as any blinding would be difficult to obtain because the participants in the intervention group are subdivided in three different subgroups (grouped according to the nurse delivering the intervention), while the non-intervention group is kept in one group. However, the analysis will comply with the statistical methods outlined in the study protocol. An interim analysis is not planned.

Obtaining LS-PGA and DLQI five times during the study gives extra strength to the analysis, so a smaller difference can be detected, if this is stable over time.

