## **Analysis methods to handle protocol non-adherence and any statistical methods to handle missing data**

Missing data on the primary outcome will be evaluated to assess the occurrence of specific missing data patterns, and if necessary, missing data will be handled by using multiple imputation. Missing effectiveness values are imputed at missing time points using values from available time points. Furthermore, missing data will not be imputed for PRO outcomes or adherence measures.

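### The expected-amount formula for secondary adherence assumes 336 days and five on-schedule BSA readings, so off-schedule final visits misplace patients near the 80% cut-off, and no rule covers a missing reading

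*Combined protocol and SAP*

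**What the plan says.** All references are to the combined protocol and SAP.

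- **Secondary adherence**: the rate is consumed amount over expected amount. The expected amount is 0.5 g/day × 48 weeks × 7 days × a weighted mean BSA, "calculated from BSA measures at baseline and at weeks 12, 24, 36 and 48", with weights 1-2-2-2-1 over 8. For the numerator, "weight of consumed drugs will be obtained at the last visit in week 48".
- **Analysis of secondary outcomes**: the rate is dichotomised, "with adherence rates above 80% considered adherent", and compared by logistic regression. The statistician is not blinded.
- **Plans to promote participant retention and complete follow-up**: "In case of non-attendance, the investigator will contact the participant by telephone and suggest a new consultation". No window or maximum delay is given here or elsewhere.
- **Eligibility criteria**: removal for non-attendance needs several missed appointments, so a patient with one missed visit stays in.
- **Analysis methods to handle protocol non-adherence and missing data**: "Missing effectiveness values are imputed at missing time points using values from available time points"; the next sentence adds that "missing data will not be imputed for PRO outcomes or adherence measures".
- **Severity of psoriasis** and **Data that is considered to be source data**: BSA is a disease severity measure, recorded together with LS-PGA.

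**The concern.** The formula is a trapezoid rule written for one schedule: five readings, 84 days apart, with weighing on day 336. The plan itself foresees departures from that schedule, and the formula allows for none.

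Two things follow. First, when the final visit moves, the numerator covers a different number of days from the denominator, so a patient near 80% can be classed by the date of attendance and not by use of the drug. Second, when an interim reading is absent, someone must decide after the fact how to fill it or whether to drop the patient, and that someone is an unblinded analyst. Package weight is the only one of the three adherence measures made by the blinded assessor, so it is worth getting right.

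**Working it through.** **1. The plan's formula.** 48 × 7 = 336 days; 1 + 2 + 2 + 2 + 1 = 8. The trapezoid area with 84-day spacing is 84 × (B0/2 + B12 + B24 + B36 + B48/2) = 42 × [B0 + 2(B12 + B24 + B36) + B48]. Since 336/8 = 42, the plan's denominator equals 0.5 g × this area. It is exact for complete, on-schedule patients, and only for them.

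**2. Final visit off schedule, constant BSA and constant daily use.** Scored rate = true rate × (336 + d)/336, where d is the shift in days. The documents give no delays, so d is assumed.

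| d (days) | Factor | True rates put in the wrong class |
|---|---|---|
| +7 | 1.021 | 78.4-80% scored adherent |
| +14 | 1.042 | 76.8-80% scored adherent |
| +28 | 1.083 | 73.8-80% scored adherent |
| -14 | 0.958 | 80-83.5% scored non-adherent |
| -28 | 0.917 | 80-87.3% scored non-adherent |

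Example: a true 78% at +14 days is scored 0.78 × 1.0417 = 81.3%.

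**3. The same on a declining profile (assumed BSA 10, 8, 6, 5, 5).** Planned denominator: 0.5 × 336 × (10 + 2 × 19 + 5)/8 = 168 × 6.625 = 1113 g. With the final visit 28 days late, the last interval is 112 days at BSA 5, which adds 0.5 × 28 × 5 = 70 g, giving 1183 g. If use keeps pace with BSA, the planned denominator overstates the rate by 1183/1113 = 1.063.

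**4. How many would change class.** This depends on an unknown distribution. If rates were roughly normal (mean 0.5-0.8, SD 0.2-0.3, assumed) and every final visit were equally late, about 3-6% would change class at 14 days and 5-12% at 28 days.

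**5. Interim visit late.** On the same profile, a week-12 reading of 8 taken 28 days late gives 0.5 × (112 × 9 + 56 × 7 + 84 × 5.5 + 84 × 5) = 1141 g, 2.5% above 1113 g. This matters less than the final visit.

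**6. One interim reading missing.** The formula returns nothing, and plausible substitutes disagree. Same profile, week 24 missing, consumption at 82% of 1113 g = 912.7 g:

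- linear bridge: 1134 g, rate 80.5% (adherent)
- last value carried forward: 1197 g, rate 76.2% (non-adherent)
- mean of the four readings: 168 × 7 = 1176 g, rate 77.6% (non-adherent)

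**7. How many lack a reading.** Suppose each of the three interim visits is missed with probability 5% or 10% (assumed). If misses are independent, 1 - 0.95³ = 14% or 1 - 0.90³ = 27% of patients lack at least one reading. If misses are fully clustered in the same patients, 5% or 10% do.

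**The case against.** Several points on the other side are sound.

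- **The rate may not be lost.** A reader might infer that one missed visit makes the rate uncomputable under the plan. That is one reading only. The bar covers PRO outcomes and adherence measures; BSA is listed as a severity measure, and the preceding sentence imputes effectiveness values. Imputing BSA first and then computing the rate is compatible with the text. What stands is that the plan does not say which sentence governs BSA as an adherence input, nor by what method.
- **The 8.3% inflation is not universal.** It needs constant BSA and constant use. It is 6.3% on the declining profile, and because participants treat only while a rash is present, a patient who is clear in the extra weeks adds no use and has no inflation.
- **Missing readings may be few.** Reminders go to all participants, and a rebooked visit still yields a BSA reading. Patients who miss repeatedly may be removed under the eligibility section. The independence figures are therefore at the high end. Rebooking, though, is exactly what shifts the dates.
- **The alternative is also an approximation.** If BSA falls from 10 to 4 by week 4 and stays there, the true mean is (7 × 4 + 4 × 44)/48 = 4.25. With the week-12 reading taken at week 16, the plan's formula gives (10 + 2 × 12 + 4)/8 = 4.75 and actual dates give (7 × 16 + 4 × 32)/48 = 5.0, which is further off. This bears on interim timing. It does not rescue a fixed 336 days when the numerator covers a different period.
- **Importance is limited.** This is one of three adherence measures, all secondary, and the prescription-registry measure is untouched.

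**Conclusion.** The point holds in a limited form. The denominator is fixed at 336 days while the numerator runs to the actual weighing date. For a final visit two to four weeks off schedule this moves the rate by roughly 4-8% in relative terms at constant use, and reclassifies patients within about 3 to 7 points of the cut-off. The rule for a missing interim BSA is ambiguous, and the choice can change a patient's class. The delays, miss rates and BSA profiles are assumptions; the documents give none.

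A reader might also infer that the arm comparison is biased, since the intervention arm has closer nurse contact. The documents do not show this: both arms have the same clinic visits at weeks 12, 24, 36 and 48 and the same reminders. Without a difference in timing by arm, the result is misclassification, not a directional error that the documents establish.

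**What to change.** In the Secondary adherence section, define the expected amount as 0.5 g × the linear-trapezoid area under the available BSA readings at their actual dates, from baseline to the weighing date. Require baseline BSA, final BSA and the package weight. In the missing-data section, state that a missed interim BSA is bridged this way and that the rate itself is not imputed. As a sensitivity analysis, repeat the comparison in patients with all five readings.

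The cost is one formula, one sentence and a few lines of code, with no new patient procedure. BSA is already entered in REDCap, but visit and weighing dates are not listed as data fields, so the sponsor should confirm that they are captured. The downside is that interpolation across a missed or delayed visit is approximate and will not always be closer to the true mean BSA.

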## **Information obtained and provided throughout the study**

At the baseline visit, the investigator will collect information from the patient on 1) current and previous use of medicine, 2) length of illness, 3) socio-economic status (marital status, educational level, days of sick leave and income), and 4) severity of disease and disease duration. The information will be used to check that the

non-intervention and intervention groups are comparable. In addition, after visit week 48, data from the Danish Health Registries will be obtained in order to have outcomes for primary adherence and costs of health service use.

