Obtaining LS-PGA and DLQI five times during the study gives extra support to the analysis phase, so a smaller difference can be detected, if this is stable over time.

Primary adherence will be assessed using data from the high-quality Danish National Prescription Registry (39), which is considered valid and reliable. Using package weight to obtain an estimate of secondary adherence is considered acceptable (40). The patient-reported adherence scale has previously been used in another adherence-trial (8).

All data fields in the REDCap tool are validated: All fields have a minimum and maximum value which helps to narrow down the input options. This means that REDCap prompts an error if a field entry does not meet certain expectations. Furthermore, at end of the trial, all fields will be validated via visual checking by a member of the research staff, in order to ensure accuracy and check that all data are within the prespecified minimum and maximum values. Proxy-reported outcomes will not be used.

The REDCap data collection tool has a built-in function that issues an immediate warning if all fields in the questionnaire have not been completed. At each visit, the investigator will check that no warnings have been issued. Furthermore, PRO assessments will not be taken from participants who discontinue or deviate from the assigned intervention protocol.

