#### **Data that is considered to be source data**

The following source data will be recorded from the patients' medical chart or from an interview and stored in REDCap (41): Duration of psoriasis, previous and current systemic, biologic, and topical treatment for psoriasis (in a two-year period prior to inclusion in the study) and socio-demographic data (relationship status, education and job status, municipality, and national origin). During the study, LS-PGA (including BSA) and the weight of consumed topical medication will be assessed by the blinded assessor. DLQI and EQ-5D will be reported by patients. The investigator will obtain data regarding the antipsoriatic drugs prescribed during the study period,

and the rate of filled first prescriptions for antipsoriatic drugs during the study period will be obtained. The trial personnel will note down the time used for consultations.

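### As written, the secondary adherence formula counts trial-prescribed drug that was never collected as drug used, and the 80% cut-off does not fit the four-grade self-report

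*Combined protocol and SAP*

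**What the plan says.** Under Adherence measures, the Secondary adherence section describes the quantity of interest as medication used, "determined by the weight of the remains in the used medication packages". The formula then sets "Consumed amount of topical drugs = Sum of weight of prescribed topical drugs" minus "sum of weight of all prescribed medication packages returned at visit week 48". A footnote to the first term gives the source of the weight: "As weighed from representative full medication packages of the prescribed topical drugs". The result is divided by an expected amount of 0.5 g per day over 48 weeks, times a weighted mean of five BSA readings.

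Collection is handled as a different outcome. Primary adherence is the "proportion of patients who collect their prescribed topical drug" from a pharmacy, and the section on effect parameters says "Primary adherence will be assessed using data from the high-quality Danish National Prescription Registry". The section on source data says "the rate of filled first prescriptions for antipsoriatic drugs during the study period will be obtained".

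The analysis section for secondary outcomes dichotomises all three adherence measures at 80%, counts rates above that as adherent, and compares the arms by logistic regression. The Patient-reported adherence section records four grades in quarters, the highest covering 76% to 100% of days with a rash.

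**The concern.** A package that was never collected cannot be returned. Taken literally, the formula adds its full weight to the first term and nothing to the second, so unfilled prescriptions look like use. For a patient who empties everything collected, the score is essentially prescribed over expected, whatever share was collected. It then describes prescribing rather than use.

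Long-term adherence is the third stated objective, and this is the only adherence measure based on the amount of drug used. Both the mean score and its 80% dichotomy would carry the error.

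The self-report has a separate problem. Its top grade holds patients on both sides of 80%, so the stated threshold cannot be computed from the data collected.

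**Working it through.** **Inputs from the documents.** Dose rate for expected use 0.5 g per day per BSA unit, 48 weeks, BSA weights 1, 2, 2, 2, 1 over 8 (Secondary adherence); 80% cut-off (analysis of secondary outcomes); self-report grades (Patient-reported adherence). The plan states no result that could be reproduced first.

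**Assumptions.** Mean BSA and the amounts prescribed, collected and returned are not given. All values of these below are illustrative. Container weight is ignored unless stated, and collected packages are taken as returned.

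**Expected use.** 0.5 × 48 × 7 = 168 g per unit of mean BSA.

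| Mean BSA | Expected (g) | 80% of expected (g) | Added per 100 g uncollected |
|---|---|---|---|
| 4 | 672 | 537.6 | 100/672 = 14.9 points |
| 6 | 1008 | 806.4 | 100/1008 = 9.9 points |
| 8 | 1344 | 1075.2 | 100/1344 = 7.4 points |

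A mean of 4 arises, for example, from a baseline of 8 and 3.43 at each later visit: (8 + 7 × 3.43)/8 = 4.

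**Overstatement.** Let P be the weight prescribed, C the weight collected, R the weight returned and E the expected use. The formula gives (P − R)/E; use of trial-prescribed drug is (C − R)/E. The difference is (P − C)/E.

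**Worked patient at mean BSA 4.** Prescribed 600 g, collected 400 g, all returned empty:
- Score: 600/672 = 89%.
- Use: 400/672 = 60%.
- The patient is classed adherent and should not be.

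If 500 g had been prescribed and none collected, the formula gives 500/672 = 74%. That is wrong, but the classification is still non-adherent.

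**When the classification changes.** Let r = P/E and c = C/P, with all collected drug used. The score is r and true use is r × c, so a patient is misclassified only if r > 0.8 and c ≤ 0.8/r:
- r = 0.9: c at most 0.8/0.9 = 89%.
- r = 1.0: c at most 80%.
- r = 1.2: c at most 0.8/1.2 = 67%.
- r = 0.8 or less: never.

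**Container weight.** If gross weights are used, the container of an uncollected package also counts as drug. With 12 packages of 60 g net at mean BSA 4 and none collected, the formula gives 720/672 = 1.07 with no container, 840/672 = 1.25 with a 10 g container and 960/672 = 1.43 with a 20 g container.

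**Self-report.** Everyone above 80% falls in grade 4, but so does everyone from 76% to 80%. No split of the four grades reproduces the stated cut-off. Grade 4 against grades 1 to 3 is the nearest, and it means 76% or more.

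**The case against.** The strongest reply is that prescribed here means in the patient's possession. The formula's second term and the Data management section both use the word for packages that are returned, and only packages in hand can be returned. The stated aim points the same way. On that reading the defect is one ambiguous word. This is plausible as intent, but the Primary adherence section, just before the formula, separates what is prescribed from what is collected, and the formula has no collection term. An analyst following the text would use prescribing records.

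Several stronger readings should not be drawn:

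- A reader might take the footnote as proof that prescriptions written are what is counted. It says only how a full package is weighed.
- A reader might infer that a patient who collects nothing would certainly score 89% in the 600 g case. Data management describes weighing once all prescribed packages have been returned, and missing adherence data are not imputed, so that patient might be treated as missing. The scoring is not stated.
- A reader might infer that the error is always upward. It is for trial-prescribed drug. However, the Economic evaluation section recognises that patients may get antipsoriatic prescriptions from general practitioners or private dermatologists. Use of such drug, if outside the prescribed sum, would be missed and push the error the other way.
- A reader might infer that primary adherence cannot expose the problem. That depends on the reading. If only first prescriptions count, the worked patient could be adherent on both measures. If the 80% cut-off applies to a per-patient rate of filled prescriptions, the same patient has 400/600 = 67% (prescriptions of equal size) and is non-adherent. A patient who collects nothing fails on either reading.
- A reader might infer a biased treatment comparison. Nothing in the documents gives non-collection by arm, so neither size nor direction is known.

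It is also fair that the example depends on its inputs. The same 600 g is 600/1008 = 60% of expected use at mean BSA 6 and 600/1344 = 45% at mean BSA 8, where the classification would not change.

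**Conclusion.** The point stands as a defect in the written definition. Following the formula literally gives a wrong value whenever trial-prescribed drug was not collected, and no other section repairs it. The inflation per 100 g follows exactly from the plan's own expected-use formula once mean BSA is fixed; how often it occurs and how many grams are involved cannot be known from the documents. Misclassification at 80% is confined to patients prescribed more than 80% of expected use, with container weight ignored. No distortion of the comparison between arms has been shown. The self-report cut-off is a separate and certain mismatch, although mainly one of definition and labelling.

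Only secondary outcomes are touched; the LS-PGA analysis and the sample size of 115 are not. The severity lies between minor and should-fix.

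**What to change.** 1. Define the first term as the full-package weight of trial-prescribed topical drugs actually collected or supplied. Take this from the Prescription Registry for the trial products, plus any free-of-charge topical supply recorded in charts. Match it to the same packages due for return, so that drug from other prescribers does not enter one term only. Trial-prescribed drug never collected contributes 0 g. Keep the 80% dichotomy and the logistic regression.
2. Define the self-report split as grade 4 against grades 1 to 3 and label it as application on 76% to 100% of days, or analyse the four grades by ordinal logistic regression.
3. As a minor addition, score collected but unreturned packages at 0% and at 100% used in a sensitivity analysis. At mean BSA 4, with 600 g collected, 400 g returned empty and 200 g not returned, the bounds are 400/672 = 60% and 600/672 = 89%.

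The cost is low to moderate. Registry data are already planned ("data from the Danish Health Registries will be obtained in order to have outcomes for primary adherence"), package weighing is planned, and consent covers linkage for medication use. The self-report change is wording only if the split is kept. However, scoring must wait for the extract after week 48, and package weights must be linked to collection data on the secure server, whereas Data management describes the transfer of clinic data as serving the economic analysis. The sponsor should confirm that the extract gives product and number of packages, and whether free-of-charge supply includes any topical drugs.
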